#### 5.15.4. Vital Signs

##### 5.15.4.1. Blood Pressure and Heart Rate

Blood and heart rate measurements and corresponding changes from baseline will be listed and summarized by treatment group, and visit using descriptive statistics.

An MMRM analysis as described in [Section 5.9.2](#), excluding Cohen’s D, will be used to compare the changes from baseline in supine blood pressures and heart rate of each dose group with the placebo group as summarized below.

Endpoint	Analysis Population	Analysis Method
Change from Baseline at all time points of supine heart rate	FAS	MMRM described in Section 5.9.2 .
Change from Baseline at all time points of supine blood pressure	FAS	MMRM described in Section 5.9.2 .

In addition, out of range vital signs occurring post-baseline will be summarized. For supine blood pressure and heart rate, records are eligible if they are post-baseline and are records chosen for analysis or if they are post-baseline and an average record. All post-baseline records are eligible for orthostatic blood pressure.

- Systolic Blood Pressure (Supine)
  - $< 90$  mmHg
  - $> 140$  mmHg and  $\leq 160$  mmHg

- $> 160$  mmHg and  $\leq 200$  mmHg
- $> 200$  mmHg
- Orthostatic Change in Systolic Blood Pressure
  - $\geq 20$  mmHg decrease upon standing compared with supine position
- Diastolic Blood Pressure (Supine)
  - $< 50$  mmHg
  - $> 90$  mmHg and  $\leq 100$  mmHg
  - $> 100$  mmHg and  $\leq 120$  mmHg
  - $> 120$  mmHg
- Orthostatic Change in Diastolic Blood Pressure
  - $\geq 10$  mmHg decrease upon standing compared with supine position
- Heart Rate (Supine)
  - $< 50$  bpm
  - $\geq 50$  bpm and  $< 60$  bpm
  - $> 100$  bpm and  $\leq 120$  bpm
  - $> 120$  bpm

Blood pressure and heart rate results, including orthostatic changes, will be listed.

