9.3.3 Secondary Endpoint/Estimand Analyses

The secondary estimand has the following attributes:

1. Treatments as randomized
2. mITT population as the population of interest
3. Change from Baseline to Week 6 in CGI-S score as the endpoint of interest
4. The population level summary of interest is the treatment differences estimated based on the least square mean and the corresponding 95% confidence interval from the MMRM model with treatment, visit, and treatment by visit interaction as fixed effect, participant as a random effect, and baseline CGI-S score as a covariate. An unstructured covariance structure will be used for the repeated measures. If the unstructured covariance matrix results in convergence issue, the heterogeneous Toeplitz covariance structure followed by the heterogeneous first-order autoregressive (AR(1)) structure will be used. When a reduced covariance matrix is used, the sandwich variance estimator will be used. The Kenward-Roger approximation will be used to estimate the denominator degrees of freedom.
5. ICEs will be addressed using the same strategies as described above for the primary endpoint

The number and proportion of participants with ≥ 1 and ≥ 2 point improvements from Baseline at the last CGI-S assessment (at Week 6 or the last assessment before discontinuation) will be summarized. A logistic regression model, with baseline CGI-S as a covariate, will be used to compare the proportion of responders in each active arm with placebo. If expected counts are < 5 , then a Fisher's Exact test will be used.

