9.3.5 Safety Analyses

Treatment-emergent adverse events will be coded according to MedDRA and summarized by treatment group, system organ class, and preferred term. Further summaries will be done by seriousness, severity, and relationship to IMP.

Heart rate and blood pressure measurements will be taken weekly at approximately 2 hours after IMP administration. The weekly measurements and corresponding changes from Baseline will be summarized by descriptive statistics. The change from Baseline will be analyzed using MMRM with treatment group, visit, and treatment by visit interaction as fixed effects and participant as a random effect, with the baseline value as a covariate. The difference between each emraclidine group versus placebo at each week will be estimated based on the least squares mean from the MMRM with the 95% CIs.

Other safety endpoints will be summarized with descriptive statistics by treatment group, including clinical laboratory assessments and metabolic parameters, and physical and neurological examination results (including body weight), suicidality assessments using C-SSRS, and EPS assessed by AIMS, SAS, and BARS.

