## 5.5. Strata and Covariates

Randomization was stratified by geographic region with two strata: United States or Other Countries.

The baseline value of each efficacy variable will be included as a covariate in the efficacy analyses.

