### **5.9.2. Main Analytical Approach**

The change from baseline to each study visit in total PANSS score will be summarized by visit and treatment group. A MMRM analysis will be used to analyze the data from all post-randomization timepoints up to Week 6 with treatment, geographic region, visit, and treatment by visit interaction as fixed effect, subject as a random effect, and baseline PANSS score as a covariate. An unstructured covariance structure will be used for the repeated measures. If the unstructured covariance matrix results in convergence issue, the heterogeneous Toeplitz covariance structure followed by the heterogeneous first-order autoregressive (AR(1)) structure will be used. The Kenward-Roger approximation will be used to estimate the denominator degrees of freedom. The difference between each emraclidine dose group and placebo at Week 6 will be estimated based on the Least Squares Mean (LSMean) difference between the treatment groups at Week 6 from the MMRM with the associated 95% confidence interval (CI) and P-value. A Cohen's D value will be derived as the ratio of the estimated difference to the population standard deviation at each visit estimated from the model (the square root of the diagonal elements of the estimated covariance matrix). The missing values are assumed to be missing at random for the main analysis, including missing due to missed visits or early termination due to COVID-19 control measures. The LSM ( $\pm$ SE) from the model will be plotted for change in PANSS total score by visit and treatment group. Similarly, the mean ( $\pm$ SD) of absolute values and change from Baseline PANSS total score will be presented by visit and treatment group.

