### **5.10.2. Main Analytical Approach**

Similar to the analysis of the primary efficacy variable, the change from baseline to each study visit in CGI-S score will be summarized by visit and treatment group. A MMRM analysis will be used with treatment, geographic region, visit, and treatment by visit interaction as fixed effect, subject as a random effect, and baseline CGI-S score as a covariate. An unstructured covariance structure will be used for the repeated measures. If the unstructured covariance matrix results in convergence issue, the heterogeneous Toeplitz covariance structure followed by the AR(1) structure will be used. The Kenward-Roger approximation will be used to estimate the denominator degrees of freedom. The difference between each emraclidine dose group and placebo at Week 6 will be estimated based on the LSMean difference between the treatment groups at Week 6 from the MMRM with the associated 95% CI and p-value. A Cohen's D value will be derived as the ratio of the estimated difference to the population standard deviation at each visit estimated from the model (the square root of the diagonal elements of the estimated covariance matrix). The missing values are assumed to be missing at random for the main analysis, including missing due to missed visits or early termination due to COVID-19 control measures. The LSM ( $\pm$ SE) from the model will be plotted for change in CGI-S score by visit and treatment group. Similarly, the mean ( $\pm$ SD) of absolute values and change from Baseline CGI-S score will be presented by visit and treatment group.

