### 5.12.2. Change From Baseline at All Time Points In CGI-S Score

The MMRM analysis described in [Section 5.9.2](#) will also be the basis for evaluating the change from baseline at all time points.

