### 5.12.3. Percentage of PANSS Responders at Week 6/Early Termination Visit

The binary outcome will be defined as having at least 30% reduction from baseline or not having a 30% reduction at Week 6 or the early termination visit. If a subject discontinues and does not have an early termination visit, the subject's last assessment will be used. Subjects who do not achieve a 30% reduction will be considered a non-responder.

A logistic regression model, with baseline PANSS and geographic region as a covariate, will be used to compare the proportion of responders in each active arm with placebo. Odd ratios will be constructed for each emraclidine treatment dose group compared with placebo and will be summarized with a 95% confidence interval. If expected counts are  $<5$ , then a Fisher's Exact test will be used.

Similarly, the analysis will be repeated by the subgroups defined in [Section 5.9.4](#).

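### The SAP's heart rate and blood pressure models take baseline PANSS as covariate where the protocol requires the variable's own baseline; weight, EPS and CGI-S responders have related reference faults

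*SAP*

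**What the plan says.** **Heart rate and blood pressure.** SAP 5.15.4.1 states that an MMRM as in Section 5.9.2 "will be used to compare the changes from baseline in supine blood pressures and heart rate of each dose group with the placebo group". Its table repeats the reference for both outcomes, and only Cohen's D is taken out. Section 5.9.2 is written for PANSS and ends its model statement with "subject as a random effect, and baseline PANSS score as a covariate". Protocol 9.3.5 plans the same kind of model for these two vital signs, with treatment, visit and their interaction "as fixed effects and participant as a random effect, with the baseline value as a covariate".

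**General rule.** SAP 5.5 says: "The baseline value of each efficacy variable will be included as a covariate in the efficacy analyses". Safety variables are not mentioned.

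**Weight and EPS.** SAP 5.15.4.2 and 5.15.8 also refer to 5.9.2 and again remove only Cohen's D. Protocol 9.3.5 gives these outcomes descriptive summaries and no model.

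**CGI-S responders.** SAP 5.13 refers both responder definitions to Section 5.12.3, which specifies: "A logistic regression model, with baseline PANSS and geographic region as a covariate". Protocol 9.3.3 specifies: "A logistic regression model, with baseline CGI-S as a covariate".

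**CGI-S change.** SAP 5.10.2 writes out the model in full, with "subject as a random effect, and baseline CGI-S score as a covariate". The summary table in 5.11 nevertheless cites 5.9.2 for this endpoint, and 5.12.2 says that the 5.9.2 analysis "will also be the basis for evaluating the change from baseline at all time points".

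**The concern.** A cross-reference to a model brings its covariate with it unless the text replaces it. For the safety models the text does not. A programmer who follows the SAP would fit change in heart rate or blood pressure with baseline PANSS on the right-hand side and leave out the baseline heart rate or blood pressure that the protocol asks for.

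The outcome is already a change score, but subtracting the baseline is not the same as adjusting for it. If the arms differ at baseline by chance, regression to the mean moves the estimated drug-placebo difference, and the interval is usually wider than it need be.

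Heart rate and blood pressure are where this matters most. Protocol 2.3 names increases in both as a potential risk, protocol 8.3.7 makes both triggers for adverse events of special interest, and protocol 2.2.3 reports a Week 6 heart rate difference from placebo of 4.4 bpm at 30 mg QD in the earlier trial.

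**Working it through.** **1. The plan's own figure.** The only precision statement is for PANSS: 93 completers per arm, at least 90% power, effect size 0.48. It reproduces. The normal approximation needs 92 per arm, and 93 give 90.5% (90.3% by noncentral t). Then 93/(1 − 0.25) = 124 per arm, and 3 × 124 = 372. The PANSS model carries its own baseline, so none of this changes. The documents give no precision target for heart rate or blood pressure.

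**2. Texts side by side.**

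| Outcome | Covariate by SAP reference | Covariate elsewhere | Status |
|---|---|---|---|
| Heart rate, blood pressure | baseline PANSS (5.15.4.1 → 5.9.2) | own baseline (protocol 9.3.5); 5.5 silent | contradicts protocol |
| Weight, EPS | baseline PANSS (5.15.4.2, 5.15.8 → 5.9.2) | none in protocol; 5.5 silent | gap in SAP |
| CGI-S responders | baseline PANSS (5.13 → 5.12.3) | baseline CGI-S (protocol 9.3.3; SAP 5.5) | contradicts both |
| CGI-S change | baseline PANSS (5.11, 5.12.2 → 5.9.2) | baseline CGI-S (SAP 5.10.2, 5.5; protocol 9.3.3) | wrong section number |

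**3. Loss of precision for a vital sign.** Let ρ be the baseline-to-follow-up correlation and k = baseline SD / follow-up SD. The documents give neither, so both are assumed. Assume also that baseline PANSS is unrelated to the vital sign, and take one visit and two arms. In units of the follow-up variance:

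- change score, not adjusted for own baseline: 1 + k² − 2ρk
- adjusted for own baseline: 1 − ρ²
- SE ratio: √[(1 + k² − 2ρk)/(1 − ρ²)], which is √[2/(1 + ρ)] when k = 1

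| ρ | k = 1 | k = 0.8 |
|---|---|---|
| 0.4 | √1.429 = 1.195 | √(1.00/0.84) = 1.091 |
| 0.5 | √1.333 = 1.155 | √(0.84/0.75) = 1.058 |
| 0.7 | √1.176 = 1.085 | √(0.52/0.51) = 1.010 |

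A simulation with 124 per arm and k = 1 gave SE ratios of 1.152 at ρ = 0.5 and 1.087 at ρ = 0.7, which agree with the formula. The mean estimated difference was zero to within simulation error under both models, so there was no bias on average.

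The k = 0.8 column matters because eligibility limits the baseline: exclusion criterion 20 removes supine pressures of 140/90 mmHg or more, and criterion 19 removes ECG heart rates below 45 or above 100 bpm.

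**4. Chance imbalance.** One unit of baseline imbalance moves the change-score estimate by ρ/k − 1 units relative to the adjusted one:

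- k = 1: −0.6 at ρ = 0.4, −0.3 at ρ = 0.7
- k = 0.8: −0.5 at ρ = 0.4, −0.125 at ρ = 0.7

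For illustration, assume a baseline heart rate SD of 10 bpm and all 124 per arm contributing. A one-SE imbalance is 10 × √(2/124) = 1.27 bpm. With k = 1 it moves the estimate by 0.3 × 1.27 = 0.4 to 0.6 × 1.27 = 0.8 bpm, which is 9% to 17% of 4.4 bpm.

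**The case against.** The best defence is that 5.9.2 is a template. It models change in PANSS, so using it for heart rate already means swapping the outcome, and swapping its paired baseline is the natural next step and agrees with the protocol. As a guess at intent this is probably right. It does not repair the text. The authors adapted the template explicitly by removing Cohen's D and left the covariate alone, whereas for CGI-S they wrote the replacement covariate out. SAP 5.5 stops at efficacy variables. The independent programming in SAP 9.4 checks results against the same words, so two programmers could agree on the PANSS version.

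The objection that the consequence is limited stands. These models lie outside H1 to H4, randomisation removes systematic bias, and the out-of-range counts and special-interest event summaries do not depend on the covariate. The objection that a restricted baseline shrinks the precision loss also stands, and the lower range reflects it.

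For CGI-S responders one can say that 5.5 already requires baseline CGI-S. That shows the intended covariate, but 5.12.3 names PANSS specifically and no other SAP section writes out the CGI-S responder model, so the conflict remains.

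A reader might infer more than the documents support:

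- *That the key secondary model is unresolved.* It is not. SAP 5.10.2 states it in full with baseline CGI-S, and 5.5 and protocol 9.3.3 agree. Nor can a CGI-S power loss be quoted, since the documents give no power for CGI-S.
- *That the weight and EPS models contradict the protocol.* The protocol names no model for them.
- *That CGI-I has the wrong covariate.* CGI-I has no baseline value, baseline PANSS is a legitimate pre-treatment covariate, and the protocol names none for CGI-I.

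**Conclusion.** Wrong as written for heart rate, blood pressure and CGI-S responders. In each case the SAP leads to baseline PANSS where the protocol specifies another covariate, and SAP Section 6 records no deliberate change. For weight and EPS, naming the own baseline is a free improvement to a model that the SAP adds. The CGI-S entries in 5.11 and 5.12.2 are wrong section numbers and leave the key secondary analysis settled.

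If the text is followed, the vital-sign estimates stay unbiased on average but become sensitive to chance baseline imbalance. The SE rises by about 8% to 20% with equal variances, or about 1% to 9% with k = 0.8, for ρ from 0.7 down to 0.4. These figures rest on assumed ρ and k and on baseline PANSS being unrelated to the vital sign. They have not been worked out separately for weight or EPS. The sample size and the tested hierarchy are untouched.

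**What to change.** - **SAP 5.15.4.1, 5.15.4.2 and 5.15.8:** state that the baseline value of the analysed variable replaces baseline PANSS in the 5.9.2 model. Extending the 5.5 sentence to the safety MMRMs would do the same.
- **SAP 5.13:** for both CGI-S responder rows, specify logistic regression with baseline CGI-S and geographic region.
- **SAP 5.11 and 5.12.2:** point the CGI-S entries to 5.10.2.

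The cost is a few lines of SAP text before unblinding. Every baseline needed is already in the schedule of assessments, so no data collection or sample size changes.

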#### 5.15.4.2. Body Weight

Body weight and corresponding changes from baseline will be listed and summarized by treatment group, and visit using descriptive statistics.

An MMRM analysis as described in [Section 5.9.2](#), except Cohen's D, will be used to compare the changes from baseline in body weight of each dose group with the placebo group. In addition, the frequency of subjects with  $\geq 7\%$  increase from baseline anytime during the treatment period will also be summarized. The highest weight increase from baseline across visits will be evaluated against the criterion  $\geq 7\%$  increase and summarized in the vital sign out of range table.

#### 5.15.4.3. Respiratory Rate and Temperature

Other vital sign measurements including respiratory rate and temperature will be listed. The frequency of subjects with out-of-range temperature and respiratory rate occurring post-baseline will be summarized. All post-baseline records are eligible for respiratory rate and temperature.

- Temperature
  - $< 36^{\circ}\text{C}$

- > 38°C
- Respiratory Rate
  - < 12 breaths/min
  - > 20 breaths/min

#### **5.15.5. Electrocardiograms (ECGs)**

ECGs and corresponding changes from baseline will be summarized by treatment group and visit using descriptive statistics.

The number and percentage of subjects who experience any post-baseline occurrence of potentially clinically significant corrected QT values using Fridericia's method (QTcF) will be summarized by treatment group. These presentations will include QTcF values > 450 to  $\leq$  480, > 480 to  $\leq$  500, and > 500 msec; or changes of > 30 to  $\leq$  60 or > 60 msec. [REDACTED]

#### **5.15.6. Physical and Neurological Examinations**

Physical and neurological examination data will be listed.

#### **5.15.7. Columbia-Suicide Severity Rating Scale (C-SSRS)**

The maximum post-baseline results from the C-SSRS will be summarized. The maximum of each subscale (suicidal ideation [Categories 1-5], suicidal behavior [Categories 6-10], suicidal ideation or behavior [Categories 1-10], and self-injurious behavior without suicidal intent) will be presented. The number of patients with suicide-related treatment-emergent events, treatment-emergent suicidal ideation, and suicidal behavior, based on a comparison of the C-SSRS at baseline and/or previous lifetime experience to maximum C-SSRS scores across all post-baseline assessments will be provided for each treatment. All C-SSRS elements will be reflected in a listing.

#### **5.15.8. Extrapyramidal Symptoms (EPS)**

The total score of each EPS assessment scale: Simpson-Angus Scale (SAS), Abnormal Involuntary Movement Scale (AIMS), and Barnes Akathisia Rating Scale (BARS), will be listed and summarized by treatment group, and visit, with the corresponding changes from baseline, using descriptive statistics.

An MMRM analysis as described in [Section 5.9.2](#), except Cohen's D, will be used to compare the changes from baseline in the total score of each scale of each dose group with the placebo group.

### **5.16. Pharmacokinetics**

All PK listings and individual plasma concentration-time profiles will be presented using the FAS population. PK summary tables, mean figures and all statistical analyses will be presented using the PK analysis set.

Serial venous blood samples were collected as described in [Section 3.3](#) and the Schedule of Assessments ([Section 9.1](#)) for PK assessment. PK collections that have an actual sampling time that deviates from the predefined collection time window (i.e., within 20% of the nominal time point [eg, within 12 minutes of a 60-minute sample]) will be flagged in the data listings and excluded from the calculation of concentration summary statistics.

Individual plasma concentrations will be presented in data listings and summarized separately using descriptive statistics (number of observations, arithmetic mean, SD, CV%, median, minimum, and maximum) by analyte, day, treatment, and time point. Individual plasma concentrations will be plotted by actual sample times on both linear and semi-logarithmic scales, by analyte, day, and treatment. Mean (+SD) plasma concentrations will be plotted with nominal sample times on both linear and semi-logarithmic scales with both treatments overlaid on the same plot by analyte.

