- x. A urine drug screen is required at Screening (full panel including opioids) and Baseline (dipstick); see the exclusion criteria for exclusions based on the urine drug screen. In addition, the urine drug screen will be conducted upon return to the inpatient facility for any participant who leaves the inpatient facility as described in [Section 4.1.2](#). Participants returning from a day pass who have a positive urine drug screen will be discontinued from the trial. The urine drug screen can be conducted at any time during the trial at the discretion of the investigator.
- y. PK samples will be obtained predose (within 15 minutes prior to dosing) and at 1, 4, and 8 hours following dosing on Day 4 and processed for plasma (2 aliquots required [primary/backup]) as described in [Section 8.4](#) and the Lab Manual.
- z. PK samples will be obtained predose (within 15 minutes prior to dosing) and at 1, 2, 4, 8, 12, and 24 hours following dosing on Day 24 and processed for plasma (2 aliquots required [primary/backup]) as described in [Section 8.4](#) and the Lab Manual.
 - aa. A single PK sample will be collected from participants at time of discontinuation; the actual date and time of sample collection will be documented.
 - bb. Future biospecimen research sample is optional and is only to be collected if signed consent is obtained from the participant. Sample can be collected at any time following confirmation of participant eligibility and prior to initiation of first dose.

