## 3.3. Pharmacokinetics

Venous blood samples will be collected in appropriately labeled tubes, at the times specified in the Schedule of Assessments ([Section 9.1](#)), to evaluate the PK of emraclidine and its metabolite CV-0000364.

All PK samples should be obtained at the exact nominal time relative to dosing. Samples obtained within 20% of the nominal time point (eg, within 12 minutes of a 60-minute sample) will not be considered a protocol deviation, as long as the exact time of sampling is captured in the source documents.

A fully validated bioanalytical method will be used to quantitate the concentrations of emraclidine and CV-0000364 (metabolite) in plasma.

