#### **5.16.1.4. Missing Data**

All missing concentration data will be presented as missing in concentration data listings and excluded from the concentration summary statistics. However, for the estimation of PK parameters for Day 24, missing predose concentrations will be imputed as the end of dosing interval (tau) concentration, where measurable. This imputation will be performed programmatically in the PK analysis input file.

Otherwise, missing results will be treated as missing and not imputed.

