### 5.16.2. Pharmacokinetic Analysis

Plasma concentration-time data will be analyzed by non-compartmental methods using Phoenix® WinNonlin® Version 8.3 or higher (Certara USA, Inc., Princeton, NJ) or SAS® (SAS Institute Inc., Cary, North Carolina) Version 9.4 or higher. The following PK parameters will be calculated on Day 24 for CVL-231 (emraclidine) and its metabolite (CV-0000364), where data permit:

PK Parameter	Definition
C max	Maximum (peak) observed concentration.
T max	Time of maximum (peak) observed concentration.
AUC 0-last	AUC from time 0 to the last measurable concentration (C last ), calculated using the linear up log down trapezoidal rule.
AUC 0-tau	Area under the plasma concentration time curve over the dosing interval, calculated using the linear up log down trapezoidal rule.

AUC0-tau will not be calculated if  $\lambda_z$  cannot be determined or is not reliable to extrapolate to tau.

Additional PK parameters may be calculated.

Actual sampling times will be used for the estimation of all plasma PK parameters, and all concentrations associated with scheduled sampling times will be included in the analysis (including concentrations collected outside predefined collection windows). Unscheduled PK samples will not be included in the estimation of PK parameters.

Plasma PK parameters for CVL-231 (emraclidine) and metabolite CV-0000364 will be presented in data listings and summarized using descriptive statistics (see [Section 5.16.1.6](#)) by analyte and treatment. Any excluded parameters will be flagged and included in the individual listings.

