- r The "Baseline/Screening" C-SSRS form will be completed for all subjects at Screening to determine eligibility and the "Since Last Visit" C-SSRS form will be completed at Baseline to ensure that the subject continues to qualify for the trial. The "Since Last Visit" C-SSRS form will also be completed at weekly time points after Baseline.
- s EPS assessments can be completed at any time during the trial, per investigator discretion, if symptoms are present.
- t Prior and concomitant medications should be recorded from Screening through the subject's last visit/contact.
- u Adverse events (serious and nonserious) should be recorded from the first dose of IMP through the subject's last visit/contact.
- v The Week 6 prolactin results will be partially blinded; the investigator will be notified if the prolactin levels exceed a predefined limit with instructions to send the subject for appropriate follow-up.

- w For women of childbearing potential only. Pregnancy tests can be performed at any time during the trial at the discretion of the investigator if pregnancy is suspected. Any urine pregnancy tests that are positive must be confirmed using a serum test.
- x A urine drug screen is required at Screening (full panel including opioids) and Baseline (dipstick); see the exclusion criteria for exclusions based on the urine drug screen. In addition, the urine drug screen will be conducted upon return to the inpatient facility for any subject who leaves the inpatient facility as described in protocol Section 4.1.2. Subjects returning from a day pass who have a positive urine drug screen will be discontinued from the trial. The urine drug screen can be conducted at any time during the trial at the discretion of the investigator.
- y PK samples (1 sample and 1 backup sample) will be taken predose (within 15 minutes prior to dosing) and at 1, 4, and 8 hours following dosing on Day 4.
- z PK samples (1 sample and 1 backup sample) will be obtained predose (within 15 minutes prior to dosing) and at 1, 2, 4, 8, 12, and 24 hours following administration of emraclidine on Day 24.

aa A single PK sample will be collected from subjects at time of discontinuation; the actual date and time of sample collection will be documented.

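### The 20% PK window lets the Day 24 24-hour sample fall after the Day 25 dose, and no rule flags or removes such a sample

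*SAP*

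**What the plan says.** Day 24 is the intensive PK day. Protocol 1.3, footnote z, reads: "PK samples will be obtained predose (within 15 minutes prior to dosing) and at 1, 2, 4, 8, 12, and 24 hours following dosing". SAP Table 4 repeats this. IMP is a single daily morning dose with no fixed clock time.

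Sampling should be at the exact nominal time, but both documents allow a tolerance. SAP 3.3 states: "Samples obtained within 20% of the nominal time point (eg, within 12 minutes of a 60-minute sample) will not be considered a protocol deviation", provided the exact time is captured; Protocol 8.4 agrees. SAP 5.16 makes the same 20% the analysis window: "within 20% of the nominal time point [eg, within 12 minutes of a 60-minute sample". Samples outside it are "flagged in the data listings and excluded from the calculation of concentration summary statistics".

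For PK parameters, SAP 5.16.2 uses actual sampling times and states that "all concentrations associated with scheduled sampling times will be included in the analysis", including those outside the window. It does not calculate AUC0-tau if the terminal slope cannot be determined or is unreliable for extrapolating to tau. Under SAP 5.16.1.4, for Day 24, "missing predose concentrations will be imputed as the end of dosing interval (tau) concentration", where measurable. SAP 5.16.1.5 covers a predose sample taken by mistake after dosing. No section covers a 24-hour sample taken after the next dose.

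**The concern.** A proportional window widens with nominal time, and at 24 h it runs past the end of the dosing interval. Median Tmax is 1.0 to 1.8 h fasted (Protocol 2.2.3), so a draw one or two hours after the Day 25 dose catches a near-peak level and is still accepted as the 24-hour value.

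Three results are exposed: the 24-hour concentration summary; the Day 24 parameters, including AUCtau, which is one of the two named PK endpoints; and any predose value imputed from the end-of-interval concentration. Because the sample is in window, nothing in the listings would mark it. The Day 25 dose time may not be available either. Protocol 6.4 records dose times on days with PK assessments, and the schedule shows a PK column for Day 24 but not for Day 25.

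**Working it through.** **1. The plan's own figure.** 0.20 × 60 min = 12 min, which matches the example in SAP 3.3 and 5.16.

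**2. The same rule at each Day 24 time.**

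| Nominal (h) | Tolerance (h) | Window (h) |
|---|---|---|
| 1 | ±0.2 | 0.8–1.2 |
| 2 | ±0.4 | 1.6–2.4 |
| 4 | ±0.8 | 3.2–4.8 |
| 8 | ±1.6 | 6.4–9.6 |
| 12 | ±2.4 | 9.6–14.4 |
| 24 | ±4.8 | 19.2–28.8 |

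Only the last window crosses the next dose. With that dose at 24 h the overlap is 28.8 − 24 = 4.8 h; it is 5.8 h if the dose is at 23 h and 3.8 h if at 25 h.

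**3. Is the order fixed elsewhere?** Footnote h of the schedule asks for assessments before dosing, but it is attached to the Day 1/Baseline column. Footnote z gives only the nominal time.

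**4. Illustrative size.** Half-life 9.4 to 12.2 h and Tmax 1.0 to 1.8 h come from Protocol 2.2.3 (single doses, healthy participants). One-compartment kinetics, steady state and a Day 25 dose at 24 h are assumptions.

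- ke = ln 2 / half-life; ka solves ln(ka/ke)/(ka − ke) = Tmax.
- Steady-state level, arbitrary units: C(t) = e^(−ke·t)/(1 − e^(−24ke)) − e^(−ka·t)/(1 − e^(−24ka)).
- A draw d hours after the Day 25 dose reads C(d) instead of C(24).

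Lowest case (half-life 12.2 h, Tmax 1.8 h, d = 0.25 h): ke = 0.0568, ka = 2.05, C(24) = 0.344, C(0.25) = 0.726. Ratio 0.726/0.344 = 2.11.

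Highest case (half-life 9.4 h, Tmax 1.0 h, d = 1 h): ke = 0.0737, ka = 4.09, C(24) = 0.205, C(1) = 1.103. Ratio 1.103/0.205 = 5.37.

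**5. AUC0-tau** by the SAP's linear-up/log-down rule, with actual times and interpolation to 24 h. In the lowest case C(12) = 0.680.

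- True 12–24 h segment (log): 12 × (0.680 − 0.344)/ln(0.680/0.344) = 5.91.
- With the late draw the profile rises, so the linear rule applies. The interpolated level at 24 h is 0.725, and the segment is 12 × (0.680 + 0.725)/2 = 8.43.
- Excess: about 2.51 on a full AUC0-24 of about 17.0, or +14.8%.

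Over half-lives of 9.4, 10.8 and 12.2 h, Tmax of 1.0 and 1.8 h, and d from 0.25 to 4.8 h, the error is +14.8% to +41.1%. In every combination the last value exceeds the 12-hour value, so the terminal-slope condition may instead leave AUC0-tau uncalculated. AUC0-last has no such condition; it comes out 16% to 57% above the true AUC0-24, partly because it then covers more than 24 h.

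**6. Mistiming alone, with no dose before the draw.** At 19.2 h the level is 1.31 to 1.42 times C(24), and at 28.8 h it is 0.70 to 0.76 times. AUC0-tau is unchanged (ratio 1.00). The AUC error comes from the intervening dose, not from the clock.

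**The case against.** The case against is substantial.

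- Sites are told to sample at the exact nominal time, participants are supervised inpatients, and the Lab Manual, which is not available here, may already fix the order. This makes the error less likely but does not close the gap in the documents.
- SAP 5.16.1.1 allows case-by-case review of events that alter the PK evaluation, and an intervening dose could qualify. But that clause is discretionary, it speaks of exclusion from descriptive statistics, and an in-window sample gives no timing flag to start the review.
- By definition, a value drawn after the next dose is not an end-of-interval concentration, so a careful analyst might not use it. SAP 5.16.2 nevertheless includes all scheduled concentrations. The imputation problem also needs a missing predose sample in the same participant.
- The model is simple: the protocol describes biphasic elimination, and its half-life and Tmax are single-dose values in healthy participants. That stands, so the percentages are illustrative.

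A reader might also infer that the predose sample has no tolerance, since 20% of time zero is zero. The documents do not support this. Both schedules give 15 minutes before dosing, SAP 5.16 refers to the schedule, and SAP 5.16.1.5 would be pointless if every predose sample were already excluded. At most a cross-reference is missing.

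**Conclusion.** The gap is real but narrow. The stated window overlaps the Day 25 dose by up to 4.8 h (dose at 24 h), and nothing requires the 24-hour sample to come first or says what to do if it does not. For an affected participant, under the assumptions shown, the 24-hour reading is 2.1 to 5.4 times too high. AUC0-tau is then 15% to 41% too high or is lost.

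Three stronger inferences are not supported. A distortion of the group means cannot be sized, because the documents give no rate of post-dose draws. A threatened trough endpoint cannot be claimed: trough is not a listed PK parameter, and exposure-response is left to a separate plan. A material bias in Cmax is not shown either: in the steady-state model the Day 25 peak equals the Day 24 peak, so the practical risk is a Tmax attributed to the wrong dose.

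PK is an exploratory objective, and the efficacy analyses are untouched. Priority is low.

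**What to change.** In SAP 5.16 and 5.16.1.5, and in Protocol 8.4:

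1. State that the Day 24 24-hour sample is in window only if drawn before the Day 25 dose, and that the Day 25 dose time is recorded.
2. Flag a 24-hour sample drawn after that dose. Exclude it from the 24-hour summary, AUC0-tau, AUC0-last, Cmax and Tmax, and from the predose imputation in SAP 5.16.1.4.
3. Keep 20% for the 1 to 12 h samples.
4. As a clarification only, have SAP 5.16 cite the existing 15-minute predose window.

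The cost is a few lines of text, one recorded time and the loss of a few late samples. No extra samples are needed.
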